2.3 Project design

The study is a human research study in which customers that are taking the collagen activator from Avea are observed for six months. The trial is in the form of a post marketing surveillance observational trial since the product has already been approved and is sold on the market. All participants are voluntarily taking the collagen activator. There is no blinding, randomization or placebo control that is taking place in the trial. The results are compared individually for each participant after the follow ups from their baseline measurements.

- The trial exposure is the Collagen activator from Avea
 - Potential participants are contacted after purchasing the collagen activator for 6 months via Avea's online shop. After successful recruitment they undergo the baseline assessment. They are instructed to only start taking the collagen activator once the baseline assessment is completed.
 - o Daily oral intake of 1 package of 11.5g diluted in water over six months, taken in the morning
- Saliva samples are taken twice (time points 0 and +6 months) to determine biological age via epigenetic methylation clock (Trume labs are the test providers and analysers)
- Skin analysis takes place at time points 0, +1 and +3 months to determine skin quality. This includes measurements of hydration, elasticity, skin thickness and density, as well as pigmentation, wrinkles, texture, UV-spots, pores, redness and porphyrins.
- Skin tests used for this are the corneometer, cutometer, ultrascan and Visia scan.
- Every month the participants receive a questionnaire regarding recent subjective changes, adverse reactions and adherence

The individual duration expected for each patient from the recruitment process onwards is about 6-7 months

- The goal is to recruit 60 healthy participants that are older than 35 years and are voluntarily taking the collagen activator for 6 months
- 2-3 weeks from being recruited to receiving a date for the baseline measurements
- Day 1 being the day of the baseline measurements
- Follow ups for the skin measurements take place +1 and +3 months from day 1
- Follow up for the saliva test takes place +6 months from day 1

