3.1 Project population, inclusion and exclusion criteria

The project population consists of healthy adults over the age of 35 years, regardless of gender or ethnicity, who are willing and able to give their informed consent to participate in the study. The total number of participants will be 60. The choice of participants over 35 years is because in younger individuals collagen is not yet depleted or only to a small extent ⁶. To ensure gender balance in the recruitment, our inclusion criteria are gender-neutral, gender-neutral language is used in all study materials and advertisements and we will engage in diverse recruitment to target a broad population.

Participants fulfilling the following inclusion criteria are eligible to participate in the study:

- Age 35 or older, regardless of gender, ethnicity or socioeconomic background
- Voluntarily purchasing the collagen activator (from Avea) for 6 months with the intend to take it on a daily basis
- Willing to fill out the questionnaires on a monthly basis.
- Willing to participate in all measurements part of the study (Skin tests & saliva samples)
- Able to appear at the baseline, 1 and 3 month follow up visits at the Dermatology clinic "Hautwerk" in Zürich.

If any of the following exclusion criteria are present, the participant will be excluded from the study:

- Underlying health conditions leading to regular intake of medication, including:
 - o Diabetes
 - o Hypertension (high blood pressure)
 - o Cardiovascular disease
 - o Asthma
 - o Chronic obstructive pulmonary disease (COPD)
 - o Arthritis
 - o Depression
 - o Anxiety
 - o Epilepsy
 - o Cancer
 - o Thyroid disorders
 - o Autoimmune diseases such as lupus or multiple sclerosis
 - o Chronic kidney disease
 - o Liver disease
 - o HIV/AIDS
 - o Chronic pain conditions such as fibromyalgia or chronic migraine.
 - 0 ...

- Chronic skin condition, independent of treatment, including:
 - o Acne
 - o Eczema
 - o Psoriasis
 - o Rosacea
 - o Skin cancer
 - ο.
- Intake of any collagen supplements 3 months prior to the screening date
- Smoking at time of recruitment or smoking up to 5 years prior to recruitment
- Pregnancy or lactating at the time of recruitment or planning to get pregnant in the following 6 months
- Insufficient knowledge of the German or English language
- Unable to give consent
- Unable to follow the procedures that are part of the study

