At the time point +6 months, a second saliva sample will be collected (time frame +/- 1 week of the +6 months time point). Participants will have received the collection kit at time point +3 by the study personnel. They will be reminded 1 week prior to the due date of the test and 1 day before, and will be informed about the exact procedures on how to perform the test and have the possibility to ask any questions to the study personnel via phone. They have to spit on a spoon and put the saliva on the provided paper and let it air dry for 45 minutes, before sending it to the investigators site (Avea Life, [name]). There the samples will be collectively sent for analysis to Trume labs once all samples from time point +6 have been collected. Storage of the samples is without risk at ambient temperature.

To minimize bias in the study population, during the recruitment process a focus will lie on individual participant attributes that could confound the data like gender, ethnicity and age and there will be efforts made to generate a broad spectrum of study participants to avoid only collecting information from one subgroup of the population. Also, all tests (saliva, skin analyses), and questionnaires are performed on all study participants and for the same duration of time. In the questionnaire we will ask for potential confounders so that we can account for them in the data analysis (e.g. being sick during study period, major changes in behavior etc.). The skin analyses will all be performed by the same person (doctor) to reduce measurement bias.

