6.2 Risk-Benefit Assessment

The benefits for participants of the projects are the following:

Participants in this study stand to benefit by receiving information about their biological age and their skin quality, which has the potential to improve their welfare and health awareness. These benefits are not only valuable to participants in the short term, but could also have important long-term health implications. By providing participants with free valuable health information, the study team is helping to promote participant welfare and ensure that the project is conducted in an ethical and responsible manner. There are only minimal risks associated with the intervention participants are exposed to and procedures included in this project. They are addressed in the following section together with the risk minimization:

Avea collagen activator (exposure)

• As of now there are no known adverse reactions associated with the product from any of the early trials and since the product has been on the market, there have been no reports of major adverse effects or reactions.

Skin analysis (Corneometer, cutometer, ultrascan (22Mhz), Visia scan

- Risk minimisation during the recruitment process through screening for any sensitivity regarding exposure to light (sunlight, UV-light etc.)
- A medical professional is accompanying the trial participant during that process and on the lookout for any adverse reactions or complications during the process
- All procedures that are part of the skin analysis are non-invasive. In rare cases they can lead to skin irritation or damage, specifically if they are used too often or with too much pressure, which our study personal will be instructed to avoid.
- All skin tests will not be performed on open wounds or skin infections.

Saliva collection

- The risks are minimized as the sample collection is non-invasive (participant spits on a clean spoon).
- The sample collection is self-administered and participants will be provided with clear and concise instructions on how to collect their saliva sample.

Analysis of saliva samples to determine biological age

- The saliva samples are collectively shipped every week (the samples that are ready) to our collaborator, Trume labs, without risk to the samples as they are stable up to one year under ambient conditions.
- For the analysis, 9 small DNA regions are sequenced, and used to determine the methylation of your DNA. Genetic information is not analyzed.

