- After the determination of biological age, the sequence data is deleted and the saliva samples are destroyed. This minimizes the risks of the data being used in any other way or of personal genetic information being revealed.
- The samples are screened upon arrival at Trume labs and in the case that a sample is contaminated or too wet, we will be informed and ask the participant to retake the saliva sample. As we ship the samples every week, in the case that a sample is contaminated it will be possible for the participant to redo the sample within 1 to 1.5 months maximum considering shipping times. The delay of the datapoint will be taken into account for the analysis.

•

Questionnaire

- The private information provided in the questionnaires will be kept confidential, following our protocol for data protection
- Contact details of trial doctor's are provided to the patients for any case of privacy concerns, mental support or language difficulties

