- Upon receiving the sample, it undergoes a visual inspection to ensure it is not contaminated or too wet.
- If the sample passes the visual inspection, DNA extraction and bisulfite conversion are performed to differentiate the methylated and unmethylated DNA.
- Small regions of DNA are extracted and sequenced to quantify a percentage of DNA methylation.
- Independent laboratory services are used to perform all sequencing procedures.
- Personally identifiable information is not provided to TruMe, they only receive encrypted information to ensure confidentiality.
- Multiple layers of encryption are used to protect the data.
- TruMe never provides your information to your employer or health insurance company.
- Individual-level information is not shared with any third party without explicit consent.
- Information is only provided to law enforcement if required to comply with a valid subpoena or court-ordered request.

Processes in place to ensure traceability of biological material:

- Upon receiving the sample, it is scanned into an internal registration system.
- The laboratory sends the resulting data to TruMe along with the barcode that came with the sample.

• TruMe does not receive personal identifiable information for participants of this study. Storage and technical requirements to be met:

• The laboratory maintains a cooling system to ensure appropriate storage of biological material.

Shipping biological material or data collected during the research project outside the research site:

- the receiver address: TruMe, Inc., [name]
- responsible person to whom materials or data are sent: [name]
- purpose of shipment: Analysis of saliva samples to get biological age
- temperature control: not necessary, stable at ambient temperatures
- participant confidentiality is guaranteed via separating Personally identifiable information (PII) and personal health information (PHI).
- Participants are being sufficiently informed and consent is obtained that their biological material is being sent to the US to the contracted laboratory (Trume labs) that performes the analysis of the saliva samples.

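### Section 3.3 ships saliva cards in one batch, section 6.2 ships them weekly, and no card is checked before the laboratory, so a repeated month-6 card is likely to miss its window and the planned six-month intake

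*Protocol*

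**What the plan says.** Two sections of the protocol give different shipping rules for the saliva cards that carry the primary endpoint.

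- **Section 3.3.** Baseline cards are dried by the medical professional at the clinic and sent together after the last baseline visit. Month-6 cards are made and dried at home, within one week either side of month 6, and posted to the investigators' site. Then: "There the samples will be collectively sent for analysis to Trume labs once all samples from time point +6 have been collected".
- **Section 6.2.** "The saliva samples are collectively shipped every week (the samples that are ready) to our collaborator, Trume labs". On that weekly schedule, "it will be possible for the participant to redo the sample within 1 to 1.5 months maximum considering shipping times". It adds: "The delay of the datapoint will be taken into account for the analysis".

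On usability, section 6.2 reads "The samples are screened upon arrival at Trume labs and in the case that a sample is contaminated or too wet", after which the participant is asked for another card. Section 7.3 describes the same step at the laboratory: "Upon receiving the sample, it undergoes a visual inspection to ensure it is not contaminated or too wet". No check is described at the clinic or at the investigators' site.

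On exposure, section 2.3 gives "Daily oral intake of 1 package of 11.5g diluted in water over six months, taken in the morning", and section 3.1 requires "Voluntarily purchasing the collagen activator (from Avea) for 6 months with the intend to take it on a daily basis". Section 2.2 defines the primary endpoint after six months of intake.

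**The concern.** The primary endpoint rests on two cards per person. If the second is unusable, the value depends on when the fault is found. Every month-6 card passes through the investigators' site, yet the fault is found only after shipment to the laboratory in the United States, possibly after a hold until the last participant's card has arrived. The repeat would then represent some later time than six months. If the participant has finished the six-month supply, it would also represent a period without the product.

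Baseline has the same weakness in the other direction. Section 2.3 tells participants to start intake once the baseline assessment is done. A baseline card found unusable at the laboratory would therefore be repeated after intake has begun, and the measured change would cover less than six months of intake.

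Section 3.3 also lists, as a safeguard against bias, that all tests are done on everyone over the same length of time. A late repeat departs from that.

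**Working it through.** **1. The plan's own figures.** The 1 to 1.5 months for a repeat comes without a breakdown and is taken as given. The sample size matters only for step 5. With effect size 0.5, one-sided 0.05 and power 0.80, a two-sample t-test needs 50.15 per group, which is the plan's 50. Then 50/0.85 = 58.8, so 59, and 50/0.80 = 62.5, so 63. All three reproduce. (A paired test needs 26.1, so 27, which is why power in step 5 is high. That is a separate matter.)

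**2. The window.** One week is 7/30.4 = 0.23 month, so the month-6 window runs from 5.77 to 6.23 months. A repeat stays inside it only if the whole cycle of shipping, screening, notice and new card takes at most 14 days (first card on the first day of the window) or 7 days (first card on the due date). Waiting for a weekly shipment can use up to 7 of those days.

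**3. Date of a repeated month-6 card, in months from day 1.**

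- Weekly rule, at the stated 1 to 1.5 months: 6 − 0.23 + 1 = 6.77 to 6 + 0.23 + 1.5 = 7.73.
- Batch rule, first enrolled: the card waits for the enrolment spread *s*, then 0.75 to 1.5 months for shipping, screening and repeat. This gives 6 + *s* − 0.23 + 0.75 to 6 + *s* + 0.23 + 1.5.

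| Case | Repeat at (months) |
|---|---|
| Weekly rule | 6.8 to 7.7 |
| Batch, first enrolled, *s* = 1 | 7.5 to 8.7 |
| Batch, first enrolled, *s* = 2 | 8.5 to 9.7 |
| Batch, first enrolled, *s* = 3 | 9.5 to 10.7 |
| Batch, last enrolled (*s* = 0) | 6.5 to 7.7 |

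Both *s* and the 0.75-month lower value are assumptions. Section 3.3 gives an August start and a last follow-up visit in December or January. If that is the month-3 visit, the last baseline falls in September or October. A spread of one to three months is compatible with this, but the protocol does not state it.

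Every row lies beyond 6.23 months and after the planned intake.

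**4. Date of a repeated baseline card.** Weekly rule: up to 1 to 1.5 months after day 1. Batch rule, first enrolled: from 1 + 0.75 = 1.75 months (*s* = 1) to 3 + 1.5 = 4.5 months (*s* = 3). Either way, intake would normally have started.

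**5. Effect on power (illustration only).** Suppose a share *f* of month-6 cards is repeated and those repeats carry no effect at all. The effect size becomes 0.5 × (1 − *f*).

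| *f* | Effect size | One-sided paired power, n = 50 |
|---|---|---|
| 0 | 0.50 | 97% |
| 2% | 0.49 | 96% |
| 5% | 0.475 | 95% |
| 10% | 0.45 | 93% |
| 20% | 0.40 | 87% |

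Even this worst case costs little power, and it dilutes towards no effect.

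**The case against.** **The hold may never happen.** A reader of section 3.3 alone might infer that every month-6 card certainly waits for the last one. Section 6.2 says otherwise, so this is a contradiction to be settled, and the longest delays arise only under the batch rule. This stands.

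**A maximum is not the usual delay.** Section 6.2 gives 1 to 1.5 months as a ceiling, and a quicker repeat is possible. This stands, so a miss of the window is likely and not certain. Step 2 shows how quick the cycle would have to be.

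**Off-product values are not planned.** It is tempting to conclude that a value taken without the product becomes the primary outcome. The documents do not say so. The six months of intake and purchase make it plausible, but participants buy the product themselves and may continue, and nothing says what happens until a repeat.

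**The delay is to be handled in the analysis.** Section 6.2 promises this. The model in section 4.1 lists only chronological age and sex as covariates, but the method may sit in a statistical analysis plan that is not at hand, so its absence is no finding. If chronological age is taken at the sampling date, the extra ageing is already covered. Still, no model term recovers a month-6 measurement that was never made.

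**Home cards need not fail more often.** Section 3.3 provides reminders, instructions and telephone support. More failures at home are plausible, but the documents give no rate for either time point.

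**Conclusion.** Sections 3.3 and 6.2 cannot both be followed. Under section 3.3, the repeat limit in section 6.2 does not hold for early participants. Under either rule, checking cards only at the laboratory makes it likely that a repeated month-6 card falls outside the protocol's own window and after the planned six months of intake, and that a repeated baseline card falls after intake has begun.

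The number of participants affected is unknown. The delays beyond 7.7 months rest on an assumed enrolment spread, and the power figures on assumed repeat rates with complete loss of effect. The harm is mainly to what the six-month value means for those few participants. It is no threat to power, and fading of an effect would not by itself produce a false positive. The correction is worth making because it is nearly free.

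**What to change.** 1. **Use one shipping rule.** In section 3.3, replace both batch shipments with the weekly shipment of ready cards in section 6.2. If batching is kept, restate the 1 to 1.5 month maximum in section 6.2.
2. **Check cards before they leave.** In section 3.3, have staff make the laboratory's visual check (dry, not contaminated) before the participant leaves the baseline visit, and on the day each month-6 card reaches the investigators' site. Any repeat is requested at once.
3. **Make late repeats visible.** For any repeat, record the actual sampling date and whether the product was still being taken. Calculate chronological age at that date. Report a sensitivity analysis without cards taken outside the window.

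Dropping late repeats from the primary analysis is not advised as the default: under the complete-case rule in section 4.2, it could remove the participant altogether. A spare card filled at the same sitting may share the first card's fault.

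The cost is about a minute of staff time per card and more frequent shipments, which section 6.2 already plans. At baseline, the card dries for 45 minutes and the visit lasts 30 to 60, so some participants may have to wait for the check. A site check will not catch every card that the laboratory rejects, and it does not guarantee a repeat inside the window. It does remove the hold and the overseas leg from the delay for the faults it finds.

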3.4 Withdrawal and discontinuation

The Sponsor or Projectleader may terminate the trial prematurely for individual participants or the participants may withdraw from the study according to certain circumstances:

- Participants can withdraw from the study if they have any concerns regarding their health or safety being compromised due to the procedures during the study or if they voluntarily stop to take the collagen activator, which no longer qualifies them to be part of the study.
 - o This includes any adverse reactions to the procedures during the study
 - o Other restrictions or reductions regarding their mental or physical health that is linked to the procedure during the trial
 - o if they withdraw their informed consent
 - o if they voluntarily decide to stop taking the "intervention"
 - Participants can be excluded from the trial in case of non-compliance
 - o Incorrect / irregular intake of the "intervention"
 - o Failing to regularly answer the questionnaire
 - o Missing out or not showing up to the appointments
 - o Not adhering to the required testing procedures

In case a participant has to withdraw or be excluded from the study, their data will not be included in the analysis (sample size is adjusted for a drop-out rate of 15%). There will be no final examination of the participant and the previously gathered material of the participant will be destroyed.

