3.2 Recruitment, screening and informed consent procedure

Recruitment will be conducted through advertising the study to Avea customers after they have bought the collagen activator in the Avea online shop for the first time. The advertisement will be uploaded in BASEC.

Potential participants are Avea customers, therefore the Avea team has access to their email addresses. The study advertisement is sent to the email address under which the order was placed. The first round of pre-selection will be done by the potential participants themselves by going through the study advertisement and the description of the trial. If a person decides they are interested in participating, they can fill out the inclusion and exclusion guestionnaire which is attached to the advertisement (via a link to a google form). In this form they enter their email address. For questions they can reach out via email to the person in charge of recruitment at Avea. The results of the google form are only visible to the Avea team member in charge of recruitment. Once that person has decided if a person is eligible to participate according to the criteria defined in section 3.1 (if uncertain the decision is made together with [name]), the answers of the google form are deleted immediately and the email address is transferred to RedCap. From then on they are considered as participants and all information is securely stored and encrypted in RedCap. Via RedCap they then receive the detailed study information. This entails the nature of the study, its purpose, the procedures involved, the expected duration, the potential risks and benefits and any discomfort it may entail. Each subject is informed that the participation in the study is voluntary and that he/she may withdraw from the study at any time and without stating any reason. The withdrawal of consent will not affect his/her subsequent medical assistance and treatment. The subjects are informed that he/she can ask any question, and consult with family members, friends, their treating physicians or other experts before deciding about their participation in the study. Enough time is given to the subjects to make a decision and to give informed consent at all times. The subjects are informed that authorized individuals may examine his/her medical records and how and for which purpose the extracted data will be used.

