- 3. Ultrascan: Ultrascan is a non-invasive device that uses high-frequency ultrasound waves (22 Mhz) to measure the thickness and density of the skin. The device works by emitting ultrasound waves into the skin, which bounce back and are recorded by the device. The time it takes for the ultrasound waves to bounce back is used to calculate the thickness of the skin. This measurement is used to assess the overall health of the skin and collagen content can be read out by it.
- 4. Visia scan: Visia scan is a non-invasive imaging system that captures high-resolution images of the skin's surface. The device uses different types of light, such as UV, polarized, and non-polarized light, to capture images of the skin at different depths. The images are then analyzed to assess various skin conditions, including pigmentation, wrinkles, texture, UV-spots, pores, redness, and porphyrins. This measurement is used to assess the overall health and quality of the skin.

At the time points +1, +2, +3, +4 +5 and +6 months of the study duration, a short online questionnaire will be sent to all participants via email, with a secure link to the REDcap online form. It will contain questions about the product intake (how many days of the months), the health status (any changes, physical or mental illness, adverse reactions), important lifestyle changes, and if the participants are still willing to continue with the study. There will also be the possibility for the participants to reach out to a medical professional or to schedule a visit.

At the timepoints +1 and +3, follow-up visits at the Dermatology clinic Hautwerk will be scheduled (time frame +/- 1 week of the +1 and +3 months time point respectively). The visit will contain the same procedures as the visit at time point 0, minus the saliva sample. The medical professional will again first check the completion of the questionnaire and assist if necessary, then take the skin scan (Visia analysis system), and the tests with the corneometer, cutometer and ultrascan. The participants have then time to rest to make sure there are no adverse reactions to any of the procedures. At time point +3, the participant will be provided with the saliva collection kit for timepoint +6 months. Each visit will be recorded by the medical professional. The total visit should take between 30 to 60 minutes.

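### Section 3.4 provides no outcome follow-up for any leaver's product reaction, and a non-serious reaction behind an exit before +1 month or between two monthly forms is not asked about

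*Protocol*

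**What the plan says.** Protocol section 3.4 lets participants leave over health concerns tied to the study procedures, or "if they voluntarily stop to take the collagen activator, which no longer qualifies them to be part of the study". The adverse reactions it names as a ground are those to the procedures: "This includes any adverse reactions to the procedures during the study". A reaction to the product is not named, although section 6.2 discusses the product and the procedures under separate headings.

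For anyone who withdraws or is excluded, 3.4 says that "their data will not be included in the analysis" and "There will be no final examination of the participant". It states no exception for adverse events. Section 3.2 adds that a participant "he/she may withdraw from the study at any time and without stating any reason".

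Adverse reactions are collected under section 3.3. At +1 to +6 months "a short online questionnaire will be sent to all participants via email, with a secure link to the REDcap online form". The form asks for days of intake, health status including adverse reactions, and "if the participants are still willing to continue with the study". Participants may also contact a medical professional or arrange a visit on their own initiative. Section 5.3 deals with serious events. Appendix 1 shows no exit or post-exit contact.

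**The concern.** Section 2.3 describes the study as post-marketing surveillance, and the monthly form asks about adverse reactions throughout. Someone who reacts badly to the product has an obvious reason to stop taking it, and under 3.4 stopping ends participation. The rule therefore bears most on the people whose experience a surveillance study would want to record.

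Two things are at stake. One is the participant: a person who leaves with an unresolved reaction has no planned contact to see whether it settled. The other is the account of tolerability: if adverse reactions are summarised only for those who stay, the summary leaves out people who stopped because of a reaction. Section 3.4 does not rule out such a summary, because its exclusion of leavers' data makes no exception for adverse events.

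**Working it through.** The protocol states no figure on this point to reproduce. The check is to follow each way of leaving through the stated procedures and see whether the person is asked about reactions, and whether anything is planned afterwards.

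**Inputs**
- Follow-up forms: +1, +2, +3, +4, +5 and +6 months, so 6 in all (section 3.3).
- Content of each form: intake days, adverse reactions and willingness to continue, asked together (section 3.3).
- Reason for leaving: not required (section 3.2), and no section invites one at exit.
- Final examination: none (section 3.4).
- Scheduled contacts after exit: 0 (section 3.4 and Appendix 1).

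**By route of exit**

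| Route | Forms received by exit | Asked about the reaction behind the exit? | Scheduled contacts afterwards |
|---|---|---|---|
| Exit declared on a monthly form | includes that form | Yes, on the same form | 0 |
| Product stopped without telling anyone | the next form still arrives, within about 1 month | Yes, if the form is answered | 0 once the exit is known |
| Exit by email, phone or in person before +1 month | 0 of 6 | No | 0 |
| Same, between form k and form k+1 (k = 1 to 5) | k of 6, the last up to about 1 month old | Not if the reaction began after form k | 0 |

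The second row assumes that forms go on being sent until the study team knows of the stop. The last two rows assume that no further form is sent once the exit is known. The protocol does not say so in terms, but forms go to participants, and 3.4 says this person no longer qualifies.

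**What the table shows**
1. Solicited capture is missing in the third row, and in the fourth row for a reaction that began after the last form. The period not asked about is at most about one month.
2. The last column is 0 in every row. The absence of planned follow-up therefore applies to every leaver, including one who has already reported a reaction on a form.

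**Scale.** Section 3.4 allows for 15% drop-out and section 4.1 for 15-20%. Of 60 participants that is 0.15 × 60 = 9 to 0.20 × 60 = 12 leavers for any reason. The protocol gives no share of these who would leave because of a reaction, or between forms, so the number affected cannot be derived.

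**The case against.** The case against has several sound parts.

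- **The monthly form covers much.** A reader might infer that a leaver's reaction is recorded only if the leaver volunteers it. The documents do not support that as a general statement. Anyone who declares the exit on the form is asked about reactions there, and someone who stops silently still receives the next form.
- **Other safeguards exist.** Participants may reach a professional (3.3), protective measures are required where health is in danger (5.2), serious events are handled (5.3), and withdrawal does not affect later medical care (3.2). These stand as partial cover. None sets out an exit question or follow-up of a non-serious reaction, and 3.3 does not say that its contact route stays open after exit.
- **Silence is not prohibition.** Section 3.4 does not forbid follow-up. The most that can be said is that none is provided for.
- **The wording of 3.4 may be about efficacy.** The examinations in this study are skin tests, the exclusion sits beside the drop-out allowance, and section 4 plans no adverse-event analysis. That is a reasonable reading, and it is why one clarifying sentence would largely settle the exclusion rule. It does not supply the missing exit question or follow-up.
- **Details may lie elsewhere.** The eCRF is not shown and the consent pages were removed, so either may already invite a reason. The schedule of assessments is shown, however, and it has no contact after exit.

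A reader might also infer from 3.4's destruction of gathered material that leavers' adverse-event records are lost. Section 7.4 keeps health-related data for 10 years, and nothing says that those records are destroyed.

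**Conclusion.** The point holds as a minor one. As written, 3.4 ends participation when the product is stopped, excludes leavers' data without an exception for adverse events, and provides no final examination. Two gaps follow: no solicited capture of a non-serious product reaction behind an exit before +1 month or between two forms, and no provision for following any leaver's reaction to its outcome.

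This rests on the reading that a person whose exit is known receives no further forms. The number affected is unknown. Safety is not an endpoint, and no efficacy result or sample size changes.

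It would be tempting to put a figure on how favourable the tolerability account would look. The documents do not allow it. They give no reaction rate among those who stay or those who leave, and they plan no adverse-event rate that the exclusion would distort.

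**What to change.** Amend section 3.4 as follows:
1. At exit, invite a voluntary reason for stopping, including any suspected reaction to the product. The right to leave without giving a reason stays as it is.
2. For a leaver with a suspected product reaction, offer, with consent, the existing REDCap form or a call until the outcome is known.
3. Limit the exclusion of leavers' data to the efficacy analysis, and state that their adverse reactions are kept and reported with those of all participants who took the product.

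The cost is a few sentences in 3.4, matching consent wording where it is not already there, one optional eCRF field, and a few calls or extra sends of a form that already exists. The downside is a small amount of voluntary contact after withdrawal. The sample size and the efficacy analysis are unchanged.
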